7.3.2.3 Patient reported outcomes

Abbreviated Profile of Hearing Aid Benefit (APHAB form A)

The APHAB form “A” questionnaire (13) from HARL (Hearing Aid Research Lab, University of Memphis, USA) is a 24-item self-assessment inventory that evaluates the benefit experienced by the subject when using hearing amplification compared to the unaided listening. APHAB produces a global score and scores for four subscales: Ease of Communication, Reverberation, Background Noise, and Aversiveness.

The subjects will complete the APHAB questionnaire at Screening/Baseline, 3 and 6 months follow up.

- At Baseline, the subjects shall complete the questionnaire prior to the Softband test, and the questionnaire shall be answered with respect to the unaided hearing, even for subjects with a previous hearing device.
- At Follow up at 3 and 6 months, the subjects shall complete the questionnaire for the aided situation (with the Investigational device).

The APHAB questionnaire is available for free and in different languages on the HARL home page.

Speech, Spatial and Qualities of Hearing Scale (SSQ-12 version)

The short form of Speech, Spatial, and Qualities of Hearing Scale questionnaire (SSQ-12) (17) from MRC Institute of Hearing Research, UK, is a scaled-down version of the 49 items SSQ questionnaire (14). It is designed to compile a sub-set of items from the longer original 49 version to represent the scale as a whole, measuring self-reported auditory disability, reflecting the reality of hearing in the everyday world. It has been shown to provide similar results to SSQ49 (17). It covers:

- Hearing speech in a variety of competing contexts
- The directional, distance and movement components of spatial hearing
- Segregation of sounds and attending to simultaneous speech streams
- Ease of listening
- The naturalness, clarity and identifiability of different speakers, different musical pieces and instruments, and different everyday sounds

The subjects will complete the SSQ questionnaire at Screening/Baseline, 3 and 6 months follow up.

- At Baseline, the subjects shall complete the SSQ questionnaire prior to the Softband test and the SSQ questionnaire shall be answered with respect to an unaided hearing, even for subjects with a previous hearing device.
- At Follow up at 3 and 6 months, the subjects shall complete the questionnaire for the aided situation (with the Investigational device).

The SSQ-12 questionnaire was approved for use in this clinical study for free by [name], former Director of MRC Institute of Hearing Research, which closed down 2018.

Health Utilities Index (HUI)

HUI® (15) is a generic preference-based system for measuring comprehensive health status and health-related quality of life (HRQoL). HUI provides descriptive evidence on multiple dimensions of health status, a score for each dimension of health and an overall health-related quality of life (HRQoL). The scoring systems provide utility (preference) scores on a generic scale where dead = 0.00 and perfect health = 1.00. HUI3 will be used in this clinical study (Questionnaire HUI23S1EN.15Q). The HUI3 classification system is comprised of 8 attributes: Vision, Hearing, Speech, Ambulation, Dexterity, Emotion, Cognition and Pain – each with 5 or 6 levels of ability/disability (18). The version in this clinical study uses a recall time of 1 week.

The subjects will complete the HUI at Screening/Baseline, 3 and 6 months follow up.

- At Baseline, the subjects shall complete the HUI questionnaire prior to the Softband test and with respect to their current hearing situation.
- At Follow up at 3 and 6 months, the subjects shall complete the questionnaire for the aided situation (with the Investigational device).

The license to use the HUI questionnaire is purchased from Health Utilities Inc., [name].

7.3.2.4 Usability

Magnet choice

At fitting the most suitable magnet for the SP shall be selected, and the instruction for use are found in Osia 2 Sound Processor User Manual shall be followed. It is important that the strength is not too weak or too strong. There are 4 different strengths, ranging from 1 to 4, strength 1 being the weakest. During the follow up visits the choice of SP magnet shall be checked and recorded. There may be a need to decrease or increase the strength depending on the subject's preference. Every time a change occurs it is important to perform a new fitting procedure according to the OFS.

Sound Processor retention

At first fitting and all follow up visits, the subjects shall estimate the experienced retention of the SP.

The estimation shall be performed using the VAS scale (visual analogue scale 100mm) with insufficient retention to the left and excellent retention to the right.

With regard to your Sound processor, please rate the overall retention by placing a single vertical line on the scale.

*Insufficient
retention*

*Excellent
retention*

Sound Processor wearing comfort

At first fitting and all follow up visits, the subjects shall estimate the experienced wearing comfort of the SP.

The estimation shall be performed using the VAS scale (visual analogue scale 100mm) with no comfort at all to the left and excellent comfort to the right.

With regard to your Sound processor, please rate the overall comfort by placing a single vertical line on the scale.

*Not comfortable
at all*

*Most comfortable
imaginable*

Daily use

At all follow up visits data regarding daily use of the sound processor will be collected.

Average hours of daily use (hours/day) during the last week before each Follow up visit shall be recorded.

Daily streaming

At all follow up visits, data regarding daily streaming using the sound processor shall be collected.

Average hours of daily streaming (hours/day) during the last week before follow up shall be recorded.

Battery lifetime

During the clinical investigation SP battery lifetime will be followed from 6 weeks post surgery. At the follow up visit, data regarding battery lifetime for the sound processor will be collected. Average hours of the battery lifetime for a single battery during the last week before each follow up visit. Subjects will be encouraged to use each battery until the “low battery” is signaled by the SP.

SoftWear Pad use

During the clinical study at first fitting and at each follow up visit, data regarding SoftWear pad use (Yes/No) for the sound processor will be collected.

7.3.2.5 Device exposure

Device exposure is information about for how long the subject is exposed to the Osia 2 Implant and the Osia 2 Sound Processor. Data is summarized from other data fields in the same case report form.

7.4 Safety Evaluations and Procedures

Subjects will be carefully monitored during the study for possible adverse events and appropriate treatment of the subject will be initiated. Any adverse events observed will be fully investigated by the investigator and documented in the CRF including assessment of seriousness, severity (mild, moderate or severe) and relationship to the medical device. The risks and anticipated ADEs for Osia 2 System, as identified in Section 8.3 of the CIP, will be assessed in the clinical study via reporting of all AEs/ADEs from the time of first subject first visit until last subject last visit. The Sponsor will be notified by automatic eCRF alerts when

events are judged as device related or serious. A safety monitor, appointed by the Sponsor, will be contacted regarding events that are uncertain, serious or unexpected.

7.4.1 Numbness

At all visits from Suture removal the subjects will be assessed for any presence of numbness over and around the implant area at Suture removal and throughout the study. The following scale will be used:

1. No numbness
2. Numbness over the implant Magnet Assembly area (inside red circle in Figure 9).
3. Numbness over the implant Magnet Assembly area (inside red circle in Figure 9) and 2 cm beyond the implant.

Numbness will be assessed by means of a pin and a cotton swab. Randomly picked locations over the implant Magnet Assembly area and from the edge of the implant and 2 cm out (beyond the implant) will be tested by gently touching the skin with the pin and the cotton swab. No sampling on the incision line or above the surface of the actuator.

The scale above shall be used to score the subject's sensation to stimulus with the pin and with the cotton swab.

[figure not shown]

Figure 9: Numbness will be measured over the implant Magnet Assembly area or over and beyond the implant Magnet Assembly area.

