#### **3.4.4.13 Implant site evaluation (numbness)**

Implant site evaluation (numbness) will be summarised by frequency and percent of:

1. No numbness,
2. Numbness over the implant Magnet Assembly area and
3. Numbness over the implant Magnet Assembly area and 2 cm outside the implant Magnet Assembly area by visit.

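### The numbness scale in Protocol 7.4.1 has no code for numbness confined to the outer 2 cm zone, although that zone is tested

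*Protocol*

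**What the plan says.** Protocol 7.4.1 requires that, from suture removal onwards, subjects are "assessed for any presence of numbness over and around the implant area". The examiner touches the skin with a pin and a cotton swab at "Randomly picked locations over the implant Magnet Assembly area and from the edge of the implant and 2 cm out (beyond the implant"). The incision line and the surface above the actuator are not sampled.

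The result goes on a three-point scale:

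- Code 1: no numbness.
- Code 2: "Numbness over the implant Magnet Assembly area (inside red circle in Figure 9").
- Code 3: "Numbness over the implant Magnet Assembly area (inside red circle in Figure 9) and 2 cm beyond the implant".

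On the two stimuli, 7.4.1 adds: "The scale above shall be used to score the subject's sensation to stimulus with the pin and with the cotton swab".

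Protocol 9.10.1 and SAP 3.4.4.13 plan frequencies and percentages of the same three categories at each visit. Their third category reads "Numbness over the implant Magnet Assembly area and 2 cm outside the implant Magnet Assembly area by visit". The SAP lists one output, Table 14.3.2, on the safety population. Neither analysis section mentions the pin or the swab.

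**The concern.** The examination covers two zones, and its stated aim is to find any numbness over or around the implant. The scale is nested: each higher code contains the one below. An examiner who finds normal sensation over the magnet assembly and numbness in the outer zone has followed the protocol but cannot record the finding correctly.

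Numbness is a named safety outcome, listed under implant site evaluation in Protocol 6.2. Code 1 for such a subject would understate how often numbness occurs. Code 2 would put it in the wrong place, and code 3 would overstate its extent. With three sites and no instruction, practice may differ between sites, and the final table would not show which choice had been made.

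**Working it through.** The documents state no figure for this outcome, so there is none to reproduce. The check lists the possible findings and sets them against the codes.

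**Zones against codes.** Each of two zones is numb or not, which gives 2 × 2 = 4 patterns.

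| Magnet area | Outer zone | Code in 7.4.1 |
|---|---|---|
| not numb | not numb | 1 |
| numb | not numb | 2 |
| numb | numb | 3 |
| not numb | numb | none |

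Three of the four patterns can be coded. The scale has no category for other findings. Figure 9 is not shown, but its caption describes numbness over the area, or over and beyond it, which is the same nesting.

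**Volume.** Numbness is scheduled at five visits (suture removal, fitting, 6 weeks, 3 months, 6 months). That makes 30 × 5 = 150 assessments, or 150 × 2 = 300 scores if pin and swab are both recorded.

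**Possible size.** The documents give no rate of outer-zone-only numbness, so the rate p at a visit is an assumption. The expected number without a correct code is 30 × p. The chance of at least one is 1 − (1 − p)^30.

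| Assumed p | Expected of 30 | Chance of at least one |
|---|---|---|
| 2% | 0.6 | 1 − 0.98^30 = 0.455 |
| 5% | 1.5 | 1 − 0.95^30 = 0.785 |
| 10% | 3 | 1 − 0.90^30 = 0.958 |
| 20% | 6 | 1 − 0.80^30 = 0.999 |

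**Pin and swab.** Four patterns for each stimulus give 4 × 4 = 16 combinations. Of these, 3 × 3 = 9 can be coded for both stimuli, and 16 − 9 = 7 include at least one score with no code. Among the 9, the two stimuli agree in 3 and differ in 6. No text says how scores that differ are to be reported.

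**Outer boundary.** Section 7.4.1 measures the 2 cm from the implant edge: "from the edge of the implant and 2 cm out (beyond the implant) will be tested". Protocol 9.10.1 and SAP 3.4.4.13 measure it from the magnet assembly area. Section 5.1.1 describes the implant as the receiver coil, the magnet assembly and the implant body. Read literally, the two starting lines differ.

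**The case against.** The strongest reply is that this is a coarse scale of extent for a descriptive table. No hypothesis, alpha level or sample size depends on it. All adverse events are recorded, investigators are to ask about them at each visit (Protocol 11.2), and Protocol 8.3 tells users to contact the investigator about numbness at the implant site. The predecessor study reported numbness as a device-related event once (Protocol 8.2) among 51 subjects (1/51, about 2%, any location). This all stands as a limit on the impact. It does not close the gap: no text requires a numbness score to be reported as an adverse event, such a report would not correct Table 14.3.2, and event reports are likely to undercount compared with systematic testing.

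It may also be said that numbness is expected to spread outward from the magnet, or that code 3 loosely means anywhere in the wider area. The documents say neither. The outer zone is sampled in its own right, and the loose reading would mix outer-only findings with findings in both zones.

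A reader might go further than the documents allow in four ways:

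- **Pin and swab scores are pooled.** This is not stated. The analysis sections are silent, and separate blocks within Table 14.3.2 are not excluded. The silence does not itself force a wrong category, because each stimulus can still be scored alone.
- **An outer-only finding must become code 1 or 3.** No rule says so, and code 2 is equally possible. The CRF and Figure 9 are not available to settle it.
- **Numbness is the only implant-site outcome in the safety analysis.** It is the only item under that label, but adverse events of special interest include certain events at the implant site (Protocol 11.1.6) and have their own table.
- **A large share of subjects would be miscoded.** The documents support no particular rate.

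**Conclusion.** The concern holds for the scale. Numbness confined to the outer zone is tested for but cannot be recorded correctly, and the same three categories carry the error into Protocol 9.10.1, SAP 3.4.4.13 and Table 14.3.2. That follows from the text alone, unless the unseen CRF provides another category.

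The size is unknown. At the assumed rates of 2% to 20% per visit, 0.6 to 6 of 30 subjects would be affected. The consequence is limited to one descriptive safety table and leaves the efficacy analyses and power untouched. The reporting of pin and swab scores is an unspecified detail, and the outer boundary is an inconsistency to reconcile. Both belong in the same correction, but neither causes the miscoding. This is a modest defect that is cheap to correct.

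**What to change.** 1. In Protocol 7.4.1 and the CRF, record numbness as yes or no for each zone. Alternatively, keep the scale and add a fourth code for the outer zone only. Either makes all four patterns recordable.
2. Use the same categories in Protocol 9.10.1, SAP 3.4.4.13 and Table 14.3.2.
3. Define the outer zone once, stating whether the 2 cm starts at the implant edge or at the magnet assembly area, and use that definition in all three sections and the Figure 9 caption.
4. Record pin and swab scores separately and show them as separate blocks in Table 14.3.2. With item 1, all 16 combinations can then be represented instead of 9.

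No extra examination is needed, since both zones and both stimuli are already tested. The cost is a small protocol, CRF and SAP edit, plus the handling of existing data. First consent was planned for August 2019 with 4 to 6 months of enrolment, so to about December 2019 to February 2020, and SAP version 1.0 is dated 26 March 2020. Many scores may therefore predate any change. They can be recoded only where source notes record the zones separately. The rest should be flagged and the table footnoted.

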7.4.2 Concomitant Medication and Therapies

All medications and treatments given, whether or not to treat AEs/ADEs, must be recorded in the appropriate section of the CRF.

Prohibited therapies are the following:

- long-term systemic use of corticosteroids

- ototoxic drugs
- radiotherapy in the area of implantation

If a subject receives a prohibited therapy each situation will be evaluated case by case and judged by the responsible investigator.

7.5 Equipment Used for Evaluation of Performance and Safety

All tests shall be performed in a sound insulated room. Equipment used for audiological testing shall be calibrated in accordance the local procedures at each clinic. A work instruction will be provided by the time of the Site Initiation Visit.

A laptop with OFS together with a user manual for the software according to current released version and a HiPro box will be provided by the sponsor.

7.6 Sponsor Role in Conduct of the Clinical investigation

The test set-up regarding speaker placement, sound room facility and software used at each clinic shall be checked and approved by the Sponsor at the latest during the Site initiation visit. Equipment used for audiological testing shall be calibrated before initiation of the study. Calibration certificates will be asked for by the Sponsor as part of the study documentation.

The sponsor will have a representative as support during the first surgery (or surgeries) as well as during first audiological testings and/or fitting.

8 RISKS AND BENEFITS OF THE INVESTIGATIONAL DEVICE AND CLINICAL INVESTIGATION

8.1 Anticipated Clinical Benefits

The Investigational device is an active implantable BCHIs combining the distinct advantages of the percutaneous and transcutaneous Baha systems. A recipient is expected to experience the following clinical benefits when using the system:

Efficient sound transmission through direct bone conduction, without the inherent medical and cosmetic drawbacks of a percutaneous (skin-penetrating) abutment.

Compared to passive transcutaneous BCHIs (e.g. the Baha Attract System), the Investigational device provides a more efficient transmission of sound, especially in the high frequency range, as the actuator (vibrator) is directly coupled to the bone, eliminating the attenuation of vibrations through the soft tissue that is inherent to the passive system. With the Investigational device it is also possible to position the transducer closer to the ear canal, which may further improve audiological outcomes. The Investigational device is designed to provide hearing benefit to patients with conductive, mixed or sensorineural hearing loss of up to 55 dB,

similar to a Power SP (e.g. Baha 5 Power) on abutment. Skin complications requiring treatment and/or precluding the use of the sound processor are relatively frequent for percutaneous devices (e.g. the Baha Connect System) due to the exposed abutment. For percutaneous abutments, daily site care is required to maintain a reaction-free skin penetration, but is not a guarantee for successful outcomes. For this transcutaneous Investigational device, the implant site is sealed and does not provide a direct path for infections. In addition, a transcutaneous system, without an abutment protruding through the skin, is often perceived as a more aesthetic option.

State-of-the-Art signal processing and wireless connectivity

The Investigational device is built around the same platform for audio signal processing and wireless functions as the Baha 5 family of Sound Processors with Bluetooth® Smart technology, made for iPhone (MFi) with support for direct audio and data streaming, and 2.4 GHz wireless technology that connects to Cochlear Wireless Accessories (e.g. MiniMic 2 and 2+, Phone clip, TV streamer, Remote control 2).

In addition to the overall clinical benefits provided by the Investigational device, participation in this clinical study is anticipated to benefit the subject by providing early, pre-market access to the latest technology within BCI Systems.

8.2 Anticipated Adverse Device Effects

The Investigational device has been designed and manufactured to ensure that all risks have been reduced as far as possible. However, certain adverse device effects (ADEs) may occur even after all state-of-the-art risk control measures have been implemented and verified.

As per section 4.2.2, safety and performance of the Osia System (predecessor device) has been tested in a prospective, multicentre clinical study. The following adverse device effects have been reported (to date) and may be relevant to the participants of this clinical study (more detail provided in the IB):

- One (1) serious adverse event (SAE) has been reported for the Osia System involving the removal of an Osia Implant due to a wound infection starting shortly after surgery: *possibly related to the procedure (reported by investigator)*.
- Forty one percent (41%) of system related adverse events (n=28) were related to the surgical procedure. These adverse events were mostly mild and transient (e.g. post-operative pain, swelling or irritation). The device-related adverse events (n=11) were reported as warmth from SP (n=2), headache (n=1), position vertigo (n=1), feeling of tension at implant site (n=1), pain (1), numbness (n=1) and change in bone conduction thresholds (3).

More information and details with regards to any risks with the use of the Investigational device is provided in the Investigator's Brochure.

8.3 Risks Associated with Participation in the Clinical investigation

Subjects participating in the clinical study are exposed to the anticipated adverse device, and or procedure related effects associated with standard Baha and Osia implant surgery and in connection with general anaesthesia.

The following potential complications and adverse effects are stated in the OSI200 Implant Physician's guide (9).

Prospective implant recipients should be advised of the following risks:

- General risks associated with surgery and general anaesthesia.
- Osseointegration failure – potential causes for failure of osseointegration include lack of adequate bone quantity/quality, trauma, infection, generalised diseases and surgical complications.
- Other medical complications that may require additional medical treatment, such as:
 - Concurrent Cerebrospinal Fluid (CSF) leakage
 - Subdural injury
 - Subcutaneous haematoma
 - Irritation, inflammation or breakdown of the skin flap; infection; and in some cases, extrusion of the device caused by the presence of a foreign body under the skin

Failure of device component parts (both external and internal) could result in the perception of an uncomfortably loud sound sensation, intermittent sound, or no sound.

Partial or full failure of the device could require removal or replacement of the implant.

While the majority of risks are associated with the surgery it cannot be excluded that soft tissue related complications may occur.

Investigators and users shall be aware of the following:

- If the user experience tightness, numbness or even pain at the implant site, or develop significant skin irritation, he/she shall stop using the sound processor and contact the investigator.
- Signs of overheating and signs of discomfort or skin irritation at the implant site.
- Occasional feedback and/or noise may occur.

